**Table 1**

Baseline characteristics	Intervention M, SD or N, %		Control M, SD or N, %		Full sample M, SD or N, %	
Age (years)	38.9	12.5	41.6	11.8	40.4	12.1
Sex						
Female	19	68	20	65	39	66
Male	9	32	11	35	20	34
Race						
White	20	71	22	71	42	71
Asian	6	21	4	13	10	17
Black/African American	2	7	4	13	6	10
Native Hawaiian or other Pacific Islander	0	0	1	3	1	2
Ethnicity						
Hispanic/Latino	1	4	4	13	5	8
Non-Hispanic/Latino	27	96	27	87	54	92
Employment Status						
Full-time a	13	46	18	58	31	53
Part-time a	5	18	6	18	11	19
Student	3	11	3	11	6	10
Not employed	5	18	3	10	8	14
Retired	2	7	1	4	3	5
Highest level of education						
Completed high school or some high school	5	18	5	16	10	17
Associate degree or trade school	8	29	6	19	14	24
Bachelor's degree	8	29	9	29	17	29
Graduate degree	7	25	11	35	18	31

Combined yearly household income						
\$25,000 or below	3	11	6	19	9	15
\$26,000-\$50,000	6	21	4	13	10	17
\$51,000-\$75,000	8	29	6	19	14	24
\$76,000-\$100,000	4	14	6	19	10	17
>\$101,000	6	21	6	19	12	20
Prefer not to say	1	4	3	10	4	7

*Sociodemographic Characteristics of Participants at Baseline*

*Note.*  $N = 59$  ( $n = 28$  for intervention and  $n = 31$  for control). Participants were on average 40.4 years old ( $SD = 12.1$ ), and participant age did not differ by condition. a Full-time reflects 32 hours or more of work per week. Part-time reflects less than 32 hours of work per week.

Table 2. Self-Reported Outcomes at 1 Month

Assessment	Intervention						Control						$p_{between}$	$p_{within}$		
	Baseline		1-month		Change		Baseline		1-month		Change					
	M	SD	M	SD	M	SD	M	SD	M	SD	M	SD				
Insomnia Severity Index	19.1	3.3	11.8	5.2	-7.34 a	1.87	18.6	3.2	11.0	4.0	-7.58 a	.84	0.88	0.001		
PROMIS Sleep Disturbance	60.6	5.9	7.9	7.9	-6.80 a	2.02	60.8	4.9	53.5	4.9	-7.28 a	.05	0.98	0.001		
PROMIS Sleep-Related Impairment	61.0	6.1	56.0	8.0	-4.97 a	1.85	60.4	6.2	53.4	8.1	-7.02 a	1.97	0.37	0.001		
General Anxiety Disorder	7.00	4.9	5.72	4.6	-1.28 a	-0.27	6.71	4.2	4.90	3.5	-1.81 a	-0.65	0.53	0.005		
Perceived Stress Scale	16.9	6.4	15.8	7.6	-1.13	1.19	16.4	6.7	15.7	6.2	-0.76	-.49	0.87	0.44		
Functional Outcomes of Sleep	32.8	3.9	35.8	4.9	+3.05 a	1.00	31.8	5.6	35.2	4.7	+3.44 a	-0.90	0.81	0.002		
Patient Health Questionnaire	7.40	3.6	5.4	3.6	-2.00 a	-0.07	7.7	3.6	4.7	3.4	-2.99 a	-0.23	0.39	0.001		

Note. Missing questionnaire data  $N=3$  in the intervention group and  $N=2$  for the control group.  $P_{between}=p$  value for the time x condition effect,  $p_{within}=p$  value for the time effect.

Table 3. Fitbit and Sleep Diary Outcomes at 1 Month

Assessment	Intervention						Control						$p_{between}$	$p_{within}$		
	Baseline		1-month		Change		Baseline		1-month		Change					
	M	SD	M	SD	M	SD	M	SD	M	SD	M	SD				
Sleep diary																
Sleep duration (h)	6.36	1.77	6.89	2.08	+0.53 a	+0.30	6.36	1.5	6.64	1.86	+.28 a	+0.34	0.25	0.046		
Wakefulness after sleep onset (m)	34.8	53.4	28.8	49.8	-6.0	-3.39	29.3	44.4	31.8	42.0	+2.4	-2.67	0.37	0.73		
Efficiency (%)	75.0	0.16	79	0.15	+0.04	-0.01	78.0	0.14	77.0	0.16	-0.01	+0.02	0.03	0.90		
Sleep latency (m)	43.2	46.2	39	42.0	-4.2	-4.69	41.4	41.4	43.2	52.2	+1.8	+10.70	0.07	0.63		
Fitbit																
Sleep Duration (h)	6.28	0.58	6.47	1.02	+0.19	+0.43	6.37	0.88	6.47	1.45	+0.1	+0.57	0.80	0.70		
Wake after sleep onset (m)	48.8	8.1	51.4	17.7	+2.6	+9.60	50.9	17.2	49.8	16.9	-0.9	-0.33	0.46	0.74		
Efficiency (%)	93.6	2.6	92.9	5.8	-0.7	+3.22	93.9	2.4	94.1	2.80	+0.2	+0.34	0.55	0.81		

*Note.* Missing data for actigraphy (n=23), missing data for sleep diaries (n= ).  $p = p_{between} = p$  value for the time x condition effect,  $p_{within} = p$  value for the time effect.

Table 4. Results of Self-Reported Outcomes at 3-Months

Assessment	Intervention						Control						$p_{between}$	$p_{within}$		
	Baseline		3-month		Change		Baseline		3-month		Change					
	M	SD	M	SD	M	SD	M	SD	M	SD	M	SD				
Insomnia Severity Index	19.1	3.3	11.2	4.7	-7.98 a	+1.36	18.6	3.2	9.3	4.5	-9.31 a	+1.29	0.360	0.001		
PROMIS Sleep Disturbance	60.6	5.9	53.7	8.0	-6.84 a	+2.16	60.8	4.9	52.4	6.5	-8.37 a	+1.67	0.478	0.001		
PROMIS Sleep-Related Impairment	61.0	6.1	56.2	9.4	-4.81 a	+3.30	60.4	6.2	52.6	9.1	-7.84 a	+2.94	0.246	0.001		
General Anxiety Disorder	7.0	4.85	7.24	5.6	+0.24	+5.06	6.71	4.2	5.13	5.4	-1.58	+5.83	0.284	0.338		
Perceived Stress Scale	16.9	6.37	17.5	7.6	+0.6	+1.23	16.4	6.7	15.0	7.8	-1.4	+1.10	0.254	0.227		
Functional Outcomes of Sleep	32.8	3.85	34.6	5.9	+1.8 a	+2.07	31.8	5.6	35.2	5.4	+3.4 a	-0.13	0.319	0.004		
Patient Health Questionnaire	7.4	3.64	7.1	4.8	-0.3 a	+1.20	7.6	3.6	5.4	4.7	-2.2 a	+1.09	0.111	0.007		

Note. Missing data n=1 at the 3-month assessment.  $P_{between}$ = *p* value for the time x condition effect,  $p_{within}$ = *p* value for the time effect.

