Variable weak magnetic frequencies are proposed to interact with neural activity by subtly altering the brain's electromagnetic environment. Results of a pilot study testing Evolv28 suggest that device users may experience reductions in perceived stress and anxiety. Given strong associations between stress, anxiety, and poor sleep quality, the application of variable weak magnetic fields may also have benefits for sleep quality. Preliminary studies have indicated that these frequencies can influence brainwave patterns associated with different sleep stages, suggesting their potential to enhance the restorative aspects of sleep. By targeting specific frequencies, it may be possible to facilitate transitions between sleep stages, potentially helping to consolidate sleep (i.e., improve sleep efficiency) and improve sleep quality.

The goal of the current study was to conduct a randomized pilot study to evaluate the efficacy of the Evolv28 device for improving sleep quality among individuals reporting poor sleep quality. If successful, this intervention could represent a novel and scalable solution to the widespread global problem of poor sleep quality and its downstream consequences.

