Patient Health Questionnaire 8: The Patient Health Questionnaire 8 is an 8-item assessment to determine the degree to which a respondent experiences depressive symptoms. Each item corresponds to diagnostic criteria for major depressive disorder, such as little interest in doing things, or trouble concentrating. Each question is scored and added together on a 4-point Likert scale. Higher scores indicate a greater severity of depressive symptoms. Scores  $\geq 10$  indicate the presence of depressive symptoms.

Sleep Diary: Participants completed items from the Consensus Sleep diary. Items include bedtime, sleep latency, number of awakenings, total duration of awakenings, final wake time and rise time. It also

provided the opportunity to comment on any unusual event that may have occurred. Using these diaries, we calculated sleep latency, sleep duration, wake after sleep onset, and sleep efficiency. Sleep diary data was cleaned (e.g., reviewed for AM/PM errors, negative sleep efficiencies and sleep efficiencies >1) diaries were considered valid if participants had at least 4 valid days completed.

Objective sleep/wake estimation: Sleep-wake data was estimated using a Charge 5 Fitbit that was worn during the baseline week, the first week of the trial, and the last week of the trial. Fitbits are comparable to research-grade actigraphy for estimating sleep duration. Fitbit data was collected and aggregated using the Fitabase platform. Fitbit-derived sleep variables included total sleep time, wake after sleep onset (WASO) and sleep efficiency (percent asleep divided by the sleep period time). Sleep periods were auto-scored, and therefore the sleep latency variable was not valid. The sleep variables were scored by the Fitbit algorithm, using the stages algorithm (with heart rate data) when possible, and if not available using the classic (movement only) algorithm. Most days both pre and post for each group were scored using the stages algorithm (>90%) and therefore all valid days were used in the analysis. To determine a valid day, we first identified the primary sleep period. Primary sleep periods <2 h were excluded if the sleep diary did not corroborate the very short sleep period. Fitbit data were considered valid if participants had at least 4 nights of valid data.

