#### Data analysis

Data were analyzed using R version 4.2.2. We utilized descriptive statistics to describe the sample statistics at baseline. Then, we conducted linear mixed models to the effect for time and time x group interaction. The primary outcome was defined as change in ISI at 1-month. We also conducted linear mixed models to examine change over time and time x group changes from baseline to 3-months. Analyses were conducted as intention to treat and all participants who completed baseline data and were randomized were included in the mixed models. We utilized chi-square tests to evaluate percentage with a response to the intervention (decrease of 6 points or more on the ISI) and remission (ISI post-intervention score  $\leq 7$ ). An a-priori power analysis, assuming a medium-to-large effect size of  $d = 0.74$ , indicated that a total sample size of 60 participants (30 per group) would provide a power of 80% to detect significant differences with a two-sided alpha level of 0.05.

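### Tables 2–4 print follow-up SD minus baseline SD as the SD of change, so the stated spread of the primary ISI change is far too small; the Fitbit rows of Table 3 also need reconciling

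*Combined protocol and SAP*

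**What the plan says.** Data analysis defines the primary outcome as the change in ISI at 1 month and takes inference from a model: "we conducted linear mixed models to the effect for time and time x group interaction". Tables 2 (self-report, 1 month), 3 (diary and Fitbit, 1 month) and 4 (self-report, 3 months) each give a mean and SD for baseline, follow-up and change in each arm, with two p values. They give no confidence interval and no standard error. No table note gives the change SD any other meaning.

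The rows that matter most here are:

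- Table 2, primary outcome: "Insomnia Severity Index 19.1 3.3 11.8 5.2 -7.34 a 1.87 18.6 3.2 11.0 4.0 -7.58 a .84 0.88"
- Table 2, anxiety, with a negative SD: "General Anxiety Disorder 7.00 4.9 5.72 4.6 -1.28 a -0.27"
- Table 3, diary WASO, with a negative SD: "Wakefulness after sleep onset (m) 34.8 53.4 28.8 49.8 -6.0 -3.39"
- Table 4, FOSQ-10, with a negative SD in the control arm: "Functional Outcomes of Sleep 32.8 3.85 34.6 5.9 +1.8 a +2.07 31.8 5.6 35.2 5.4 +3.4 a -0.13"
- Table 4, anxiety, which does not follow the general pattern: "General Anxiety Disorder 7.0 4.85 7.24 5.6 +0.24 +5.06"

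For the Fitbit, Measures (Objective sleep/wake estimation) defines "sleep efficiency (percent asleep divided by the sleep period time". Table 3 prints sleep duration, WASO and efficiency side by side.

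The Introduction states the aim as to "conduct a randomized pilot study to evaluate the efficacy of the Evolv28 device".

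**The concern.** An SD cannot be negative, yet some entries in the change SD column are, and many carry explicit plus or minus signs, as the result of a subtraction would. The SD of a paired change depends on both SDs and on the correlation between the two measurements. The absolute difference of the two SDs is its mathematical floor, reached only when the correlation is exactly 1. A column of SD differences therefore understates the spread of change in every row it covers.

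This column is the only stated measure of the spread of change. Because the study calls itself a pilot, a reader may use it to build a confidence interval or to size the next trial. The ISI entries are positive, so nothing in that row warns the reader.

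The Fitbit question is separate: sleep time, wake time and efficiency are tied together by the definition in Measures, and the printed values do not appear to fit it.

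**Working it through.** **1. Reproducing the printed column.** There are 21 rows × 2 arms = 42 entries. Follow-up SD minus baseline SD was compared with each, with a tolerance equal to the sum of the half-units of the three printed figures.

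- ISI, 1 month: 5.2 − 3.3 = 1.9 (printed 1.87); 4.0 − 3.2 = 0.8 (printed 0.84).
- ISI, 3 months: 4.7 − 3.3 = 1.4 (printed 1.36); 4.5 − 3.2 = 1.3 (printed 1.29).
- All entries: 37 of 42 match.
- Three misses are diary minutes: −3.39 against −3.6, −2.67 against −2.4, −4.69 against −4.2. The diary SDs for WASO and latency are all multiples of 0.6 min, which is what hours rounded to 0.01 and then converted would give. Two such roundings allow about 0.6 min, and with that allowance 40 match.
- The other two misses are GAD-7 at 3 months: 5.06 against 0.75 and 5.83 against 1.2.
- Negative entries: 6 in Table 2, 5 in Table 3 and 1 in Table 4, so 12 of 42.

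**2. What the entries would imply as real SDs.** With baseline SD a, follow-up SD b and change SD s, the implied correlation is (a² + b² − s²)/(2ab). Over the 40 entries, without any conversion allowance, the minimum is 0.9957, and some exceed 1 through rounding. For the ISI at 1 month:

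- intervention: (10.89 + 27.04 − 3.50)/34.32 = 1.003
- control: (10.24 + 16.00 − 0.71)/25.60 = 0.997

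The two 3-month GAD-7 entries give 0.54 and 0.28, so they are possible change SDs. The column probably mixes two quantities.

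**3. Plausible size for the ISI at 1 month.** Change SD = √(a² + b² − 2ρab). The correlation ρ is not in the documents, so a range is assumed. From the Table 1 and Table 2 notes, n = 28 − 3 = 25 and 31 − 2 = 29. SE = √(s₁²/25 + s₂²/29). The difference in change is −7.34 − (−7.58) = 0.24. The 95% CI uses t with 52 df (2.007).

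| Basis | SD, intervention | SD, control | SE of difference | 95% CI |
|---|---|---|---|---|
| Printed | 1.87 | 0.84 | 0.405 | −0.6 to 1.1 |
| ρ = 0.7 | 3.73 | 2.88 | 0.918 | −1.6 to 2.1 |
| ρ = 0.5 | 4.56 | 3.67 | 1.138 | −2.0 to 2.5 |
| ρ = 0 | 6.16 | 5.12 | 1.556 | −2.9 to 3.4 |

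The SE from the printed SDs is too small by a factor of 0.918/0.405 = 2.3 to 1.556/0.405 = 3.8. The pooled SD is 1.41 from the printed values, against 3.30 (ρ = 0.7) to 5.62 (ρ = 0). The squared ratio, which is the factor by which a trial sized on the printed SDs would fall short, is about 5.5 to 16.

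**4. Comparison with the printed p values.** This uses a two-sample t on the changes as an approximation to the mixed model.

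- ISI, 3 months: the difference is −7.98 − (−9.31) = 1.33. The printed SDs give t = 3.8, p = 0.0003 (28/30 participants; 27/31 gives practically the same p, and the arm of the one missing participant is not stated). The table prints 0.360. Change SDs at ρ = 0 to 0.3 give p = 0.37 to 0.29.
- PROMIS Sleep-Related Impairment, 1 month: the printed SDs give p = 0.0002; the table prints 0.37.
- ISI, 1 month: 0.24/0.405 = 0.59, p = 0.56; the table prints 0.88. Read backwards, p = 0.88 implies an SE of about 0.24/0.152 = 1.6 (1.5–1.7 with rounding).

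The printed p values did not come from this column.

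**5. Fitbit rows.** The natural reading of the definition is efficiency = sleep time/(sleep time + WASO), with hours × 60:

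| | Calculation (min) | Implied | Printed |
|---|---|---|---|
| Intervention, baseline | 376.8/(376.8 + 48.8) | 88.5% | 93.6% |
| Intervention, 1 month | 388.2/(388.2 + 51.4) | 88.3% | 92.9% |
| Control, baseline | 382.2/(382.2 + 50.9) | 88.2% | 93.9% |
| Control, 1 month | 388.2/(388.2 + 49.8) | 88.6% | 94.1% |

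The gap is about 4.6 to 5.7 percentage points. If duration already includes wake time, the implied value falls to about 87% and the gap widens. The control WASO change should be 49.8 − 50.9 = −1.1, but −0.9 is printed; rounding allows at most 0.15.

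**The case against.** The strongest reply is that this is a descriptive slip with no demonstrated effect on inference. The p values come from mixed models, the baseline and follow-up SDs stand beside every entry, and nothing in the documents says that a later trial or interval will use the column. That is right about the inference, and the shortfall factor for a next trial is illustrative. It does not make the column correct.

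The p-value comparison can also be challenged. A mixed-model p need not equal a t-test of the raw difference. PROMIS Sleep Disturbance at 1 month shows the limit: a difference of 0.48 with p = 0.98 would imply an SE of about 19, while the printed baseline and follow-up SDs allow at most about 3.3 even at a correlation of −1. This stands, so the 1-month ISI comparison and the SE of 1.6 drawn from it are only supporting evidence. That SE corresponds to a correlation of roughly +0.14 to −0.24, well below the 0.7 end of the assumed range, so the two do not pin down one value. The 3-month ISI row is much clearer. The negative entries and the subtraction pattern establish the error without any p value.

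The pattern is not universal: two GAD-7 entries depart from it, and three diary entries need an unstated unit conversion. The implied correlations of at least 0.9957 do not depend on that conversion.

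On the Fitbit rows, Measures says the variables were scored by the device's algorithm and gives no explicit formula with WASO, and a ratio of group means is not a mean of ratios. A vendor efficiency field could explain the gap. The result therefore supports a request to reconcile, not a corrected estimate. The 0.2-minute WASO slip is trivial in size.

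**Conclusion.** The concern holds. Apart from the two 3-month GAD-7 entries, the change SD column in Tables 2–4 holds differences between SDs and is wrong as labelled, including for the primary outcome. Its being wrong rests on no assumption; how far it is wrong depends on the within-person correlation, which the documents do not give. Over correlations of 0 to 0.7, the printed ISI change SDs at 1 month are too small by a factor of about 2 to 3.3 in the intervention arm (3.73/1.87 to 6.16/1.87) and 3.4 to 6.1 in the control arm (2.88/0.84 to 5.12/0.84).

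The printed SDs give an interval for the ISI difference that is falsely narrow. The null primary result and the trial's own sample size are not called into question.

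For the Fitbit, the stated definition, duration, WASO and efficiency cannot all hold under the natural reading. The documents do not show which is wrong.

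**What to change.** - In Tables 2–4, replace the change SD column with the SD of each participant's own change, or with model-based SEs labelled as such. Recompute the two 3-month GAD-7 entries as well, so that the column holds one quantity.
- Preferably add the between-arm difference with its 95% CI, at least for ISI at 1 month.
- Check the Fitbit source data to find whether the definition in Measures, the duration, WASO or efficiency is wrong. If a vendor-scored efficiency was used, correct the definition. Refit only if an analysed variable proves wrong.
- Correct the control Fitbit WASO change.
- While the tables are open, check two other cells. The Table 2 PROMIS Sleep Disturbance 1-month intervention mean is printed as 7.9, whereas 60.6 − 6.80 = 53.8. Diary efficiency in Table 3 mixes percentages for the means with fractions for the SDs and changes.

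The cost is a recalculation of table columns from data in hand. The stated spread of change will become larger; correcting the SD column needs no refit and is not expected to change the primary conclusion.
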